Postoperative pain treatment with paracetamol, NSAID and morphine according to local guidelines.

PONV profylaxis:

I.v. dexamethason 8 mg routinely

Data collection

Perioperative data collection that will be noted in CRF:

Type of operation with operation code

Batch-number, expiration date, used and surplus quantities of rocuronium and sugammadex, TOF values (NMB sheet)

Body temperature measured immediately after intubation and again immediately before extubation

Size of hernia defect measured during operation just before the defect is sutured

Surgical ratings on 5 point scale

Operating time (from first incision to last suture)

Number of sudden abdominal contractions and episodes with “tight” abdomen

Need for additional NMB to optimize surgical conditions

Postoperative registration:

Number of patients with recurrences of hernias 2 years after herniotomy.

Statistics:

Eligible patients and excluded patients will be registered at a screening list.

Data from all randomized patients, who receive the intervention, will be included in the intention-to-treat analysis.

Patients, included in the intention-to-treat analysis, but who are categorized as major violation, will be excluded from the per-protocol analysis.

Normal distributed variables will be expressed by means and standard deviation; variables that are not normal distributed will be expressed by medians and interquartile range and the Mann-Whitney U test used for comparison of the median values.

Fisher's exact test will be used at comparisons of percentages. A p value < 0.05 is considered significant.

As the study is a crossover trial, it is necessary to test for a possible period effect and a treatment period interaction. To detect a possible period effect a two sample t test to compare the differences between the periods in the two groups of patients will be carried out. If there is no general tendency for patients to do better in one of the periods, we assume that the mean differences between the periods to be of the same size but with opposite signs.

To investigate the possibility of a treatment-period interaction a two sample t test will be carried out by noticing, that in the absence of an interaction, the patients response to the treatment will be the same regardless of the order in which it is received.

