If there is no period effect and no treatment-period interaction the analysis of the data regarding the primary outcome will be done by performing a Wilcoxon signed-rank sum test on all 34 patient's data (differences in workspace between the two treatments).

Primary outcome:

Improvement of surgical workspace estimated as the difference between the workspace (rated on a 5-point scale) during deep NMB and the workspace without NMB. Ratings are performed in the same patient during stable pneumoperitoneum at 12 mmHg.

Sample size calculation:

With a clinical relevant decrease of surgical workspace of 1 on the rating scale, an expected standard deviation of 2, type 1 error 0.05 and power 0.80, we calculated the sample size of 34 patients in total.

Up to 50 patients can be included to have an evaluable primary outcome in 34 patients.

Risks, side-effects and events:

Sugammadex: According to the Danish Medicine Agency's product summary, the side effects are as follows:

Very common (> 10%)	Taste disturbances.
Common (1-10%)	Anesthesia complication
Not common (0,1-1%)	Consciousness during anesthesia. Allergic reactions.

Laparoscopic herniotomy is done at Gentofte Hospital with an intraabdominal pressure at 12 mmHg without use of muscle relaxation for intubation and in some cases with use of bolus of muscle relaxation decided by the attending anesthetist. Patients allocated to group DEEP will receive rocuronium in a dose corresponding to a deep neuromuscular blockade (PTC < 8) after intubation. It is not regarded as a disadvantage to use large doses of muscle relaxation, since the effect is fully reversed by sugammadex at the end of surgery.

Registration of adverse events:

Patients will be observed during their stay at the hospital and will be contacted by telephone on first and seventh postoperative day. Possibly adverse events during this period will be reported. Finally the patient's case files will be reviewed for reports of adverse events at 17-21 days after operation.

The patients are encouraged to contact the local investigator, if they suspect any adverse events in connection with the trial and are treated according to applicable clinical principles and guidelines in the department.

Adverse events are registered as of the time when the patient is signing informed consent and the intravenous anesthetic is administered. All events are followed up until the final diagnosis or cause is established, and this is registered on the CRF.

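### The primary signed-rank test is specified only if two pre-tests are negative, and no primary analysis is named if either is positive

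*Combined protocol and SAP*

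**What the plan says.** The Statistics section says that, because the trial is a crossover, "it is necessary to test for a possible period effect and a treatment period interaction". Both are two-sample t tests between the sequence groups. The only significance level given is the general one: "A p value < 0.05 is considered significant".

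For the period test, the plan expects, if there is no period effect, "the mean differences between the periods to be of the same size but with opposite signs". For the interaction test it names no variable. It says only that, without an interaction, "the patients response to the treatment will be the same regardless of the order in which it is received".

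The primary analysis follows as a conditional sentence: "If there is no period effect and no treatment-period interaction the analysis of the data regarding the primary outcome will be done". The method named there is the signed-rank test of within-patient treatment differences, using every one of the 34 patients. No sentence covers the case where a pre-test is positive. The Mann-Whitney and Fisher sentences in the same section are general rules for comparing medians and percentages. They are not tied to the paired primary outcome.

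The sample size calculation uses a 1-point difference and a standard deviation of 2, with "type 1 error 0.05 and power 0.80, we calculated the sample size of 34 patients in total". It makes no allowance for the condition.

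**The concern.** If a pre-test is positive, the trial's only primary outcome has no pre-specified test. Someone must then choose one with the ratings in hand, and several choices are plausible: the signed-rank test anyway, a period-adjusted test, or a comparison of first ratings only.

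The condition also does not do what a reader would want of it.

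- A period effect is no reason to withhold the crossover analysis, because it can be adjusted for in the same patients.
- A negative interaction test with 34 patients does not show that carry-over is absent.

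Finally, the interaction test is not defined well enough to run. If it compares each patient's sum of two ratings between groups, it is a second, separate condition. If the patient's response means deep minus none, it repeats the period contrast and there is in effect one condition.

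**Working it through.** **Inputs from the documents.** Difference 1, standard deviation 2, alpha 0.05, power 0.80, N = 34 (Sample size calculation); 1:1 allocation (Randomization), taken as 17 per sequence; pre-test level 0.05 (Statistics). **Assumptions.** The standard deviation is that of the within-patient difference, the primary test is two-sided, and ratings are normal with within-patient correlation 0 or 0.5. The sizes of period effect and carry-over are not in the documents.

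**1. The plan's sample size.** For a paired t test the noncentrality is √n × 1/2. Power is 0.795 at n = 33 and 0.808 at n = 34, so N = 34 reproduces. This supports reading 2 as the standard deviation of the difference.

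**2. How often the condition fails.** A period effect π adds π to every second rating. Deep minus none then shifts by +π in Group A and −π in Group B, so the groups differ by 2π. The standard error is 2 × √(2/17) = 0.686, on 32 degrees of freedom. If the interaction test uses patient sums, it adds a near-independent 5% chance of a positive result.

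| Assumed π | Noncentrality 2π/0.686 | Fails: one contrast | Fails: sums added, 1 − (1 − p) × 0.95 |
|---|---|---|---|
| 0 | 0 | 0.050 | 0.098 |
| 0.25 | 0.729 | 0.109 | 0.154 |
| 0.5 | 1.458 | 0.293 | 0.328 |

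Simulation (10,000 to 20,000 trials per scenario) agrees: 0.048–0.052 and 0.093–0.098 at π = 0; 0.103–0.113 and 0.147–0.156 at 0.25; 0.290–0.299 and 0.324–0.333 at 0.5. With ratings rounded and limited to 1–5, the rates at π = 0 are 0.052 and 0.099.

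**3. Power and type I error (simulated).** With a 1-point effect and π = 0:

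- Signed-rank test without the condition: 0.78 to 0.79.
- Condition met and signed-rank significant: 0.71 (sums) to 0.75 (one contrast).
- Empty branch filled with the period-adjusted rank-sum test: 0.78 to 0.79 overall.

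With no treatment effect, the condition is met and the test significant in 0.042 to 0.047 of trials, so there is no inflation.

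**4. What a negative interaction test shows.** Suppose a 1-point carry-over into Group B's second rating.

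- On deep minus none, or on sums at correlation 0, the noncentrality is 1/0.686 = 1.458 and the power is 0.29.
- On sums at correlation 0.5, a difference SD of 2 implies a single-rating variance of 4. The SD of the sum is then √(2 × 4 × 1.5) = 3.46, the noncentrality is 1/(3.46 × √(2/17)) = 0.842, and the power is 0.13.

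In simulation both pre-tests are still negative in about 51% to 72% of such trials, while the estimated effect is halved from 1.0 to 0.5.

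**5. What a period-adjusted test costs.** Let D be second minus first rating. Its mean is effect + π in Group A and −effect + π in Group B, so A minus B is twice the effect and π cancels. The noncentrality is 2/0.686 = 2.915, the same as √34/2 for the paired test. Simulated rank-sum power is 0.777–0.785 against 0.781–0.790 for the unconditional signed-rank test at π = 0 (0.775 against 0.785 on 1–5 ratings), and 0.779–0.786 against 0.765–0.772 at π = 0.5.

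**The case against.** **Power.** A reader might infer that the plan's power falls to 0.71–0.75. The documents do not support that. The figure counts every trial with a positive pre-test as a failure, and the plan never says so. It is close to 0.79 multiplied by the 0.90 to 0.95 chance that the condition is met, and a rank-sum fill loses nothing. It also depends on the planned standard deviation. This objection stands, so the firm figure is how often no test is named.

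**Type I error.** A reader might also infer inflation. The rule as written does not cause it. Only if whichever of the signed-rank, rank-sum or first-period test came out significant were reported would the overall rate reach 0.052 to 0.073 with no period effect. That is an illustration of what the gap allows, not a property of the plan.

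**Carry-over.** That a non-significant test does not prove absence is true of any crossover. Here Group A starts with saline, and Group B is re-rated only after sugammadex and full recovery on TOF monitoring (Groups). The documents give no ground for claiming that carry-over occurs, and the 1-point figure is hypothetical. What stands is that the interaction test cannot serve as the safeguard it is used for.

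**Simpler repair.** Running the named signed-rank test regardless would also close the gap. That is correct. It is the minimal repair, although it is not adjusted for period.

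**Conclusion.** The point holds as a gap in pre-specification. The only named primary test depends on two negative pre-tests, and followed exactly the plan leaves the primary outcome without a test in about 5% to 10% of trials even when nothing is wrong. The range reflects the undefined interaction variable. An assumed period effect of 0.25 point raises it to about 10% to 16%, and 0.5 point to about 29% to 33%.

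These rates assume 17 per sequence, a standard deviation of the difference of 2, pre-tests at 0.05, and a period test on sign-reversed differences. The plan's wording on opposite signs points to that version without stating it. No loss of power and no inflation of type I error follows from the documents themselves. The gap should be closed before analysis because it concerns the sole primary test and costs almost nothing to repair.

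**What to change.** Delete the condition and state one unconditional primary analysis, for example:

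*For each patient in the intention-to-treat set with both ratings, D is the second minus the first workspace rating. D is compared between Group A and Group B by a two-sided Wilcoxon rank-sum test at 0.05, with correction for ties. The treatment effect is half the difference in mean D (A minus B), with its 95% confidence interval.*

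The mean is preferable to a halved Hodges-Lehmann shift, which on integer ratings from 1 to 5 moves in 0.5-point steps. That is coarse against a relevant difference of 1 point.

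Write the other two contrasts as formulas and report each with a 95% confidence interval and no decision rule:

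- Period effect: half of the between-group difference (A minus B) in deep minus none.
- Carry-over: the between-group difference (A minus B) in the patient's sum of two ratings.

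State that period adjustment does not remove carry-over bias.

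The minimal alternative is to run the signed-rank test whatever the pre-tests show. At an assumed 0.5-point period effect its power is about 0.77, against about 0.78 to 0.79 for the rank-sum test.

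Cost: wording in the Statistics section only. The 34 patients are kept, and at most about 1 to 1.5 percentage points of power are lost if there is no period effect.

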Investigator being the sole Sponsor has to comply with all regulatory and legal requirements as far as monitoring and data collection is concerned by following the latest Executive Order on Good Clinical Practice for Clinical Trials Involving Human Medicine (In Danish: "Bekendtgørelse om god klinisk praksis i forbindelse med kliniske forsøg med lægemidler på mennesker").

Reporting Procedures for Exchange of Adverse Event Information.

(i) For purposes of this Protocol and Agreement the below terms shall be defined as follows:

"Adverse Event" or "AE" shall mean any untoward medical occurrence in a Study subject who is administered the Study Drug regardless of whether or not a causal relationship with the Study Drug exists. By way of example and without limitation, an AE can be any unfavorable and unintended sign (for example, an abnormal laboratory finding), symptom, or disease temporally associated with the use of the Study Drug.

"Device Deficiency" shall mean inadequacy of a Study Drug device related to its identity, quality, durability, reliability, safety or performance, such as malfunction, misuse or use error and inadequate labeling.

Protocol
The hernia study
September 16. 2016

"Incident" shall mean any malfunction or deterioration in the characteristics and/or performance of a Study Drug device, as well as any inadequacy in the labeling or the instructions for use which, directly or indirectly, might lead to or might have led to the death of a patient, or user, or of other persons or to a serious deterioration in the state of health.

"Medical Device Event" shall mean any malfunction or deterioration in the characteristics and/or the performance of a Study Drug device, as well as any inadequacy in the labeling or the instructions for use which led to or could have led to an untoward event for the user or any other person.

"Serious Adverse Event" or "SAE" shall mean any untoward medical occurrence in a Study subject who is administered the Study Drug that results in death, a life-threatening drug experience, requires inpatient hospitalization or prolongation of existing hospitalization, results in persistent or significant disability/incapacity, or is a congenital anomaly/birth defect, cancer, or is a new cancer if the cancer is the condition of the study, or overdose. Other important medical events that may jeopardize the patient or may require intervention to prevent one of the outcomes listed previously should also be considered "serious".

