provided to any inspector. In the event the regulatory authority requests or requires any action to be taken to address any citations, Principal Investigator and Institution agree, after consultation with MSD, to take such action as necessary to address such citations.

F. A copy of all 15 Day Reports and Annual Progress Reports / Development Safety Update Report (DSUR) are to be submitted as required by the applicable regulatory authority by the Principal Investigator. Principal Investigator agrees to cross reference this submission according to local regulations, to the Study Drug number (IND, Clinical Study Authorization (CSA)/EudraCT approval number, etc) at the time of submission. Additionally Principal Investigator agrees to submit a copy of these reports to MSD (Attn: Global Safety; [contact]) at the time of submission to the appropriate regulatory agency.

G. MSD may provide the Principal Investigator and Institution, at Study initiation and on an ongoing basis, with information regarding the Study Drug, including but not limited to safety information. The Principal Investigator and Institution agree to hold this information in confidence.

H. Principal Investigator & Institution accept to follow the latest Executive Order on Good Clinical Practice for Clinical Trials involving Human Medicine (In Danish: Bekendtgørelse om god klinisk praksis i forbindelse med kliniske forsøg med lægemidler på mennesker").

Principal Investigator and Institution accept also to report the serious adverse reactions and unexpected non-serious adverse reactions discovered within 2 working days to MSD att: Pharmacovigilance by [contact].

Side effects/events that will *not* be registered:

In general, side effects and events that are typically seen in connection with the normal course of anesthesia and operation will not be registered and reported to the Danish Medicines Agency. In this protocol side effects/events (AE) will be defined in the form of expected changes in pulse and blood pressure as a result of the anesthesia. Pulse and blood pressure values (measured 3 repeated times within a 10-minute period) that deviate less than +/- 30% of the starting level will thus be accepted and not registered. Side effects/events that may be ascribed to the operation with certainty, for example, pain in the surgical wound or wound infection will not be registered. Side effects/events that with certainty have arisen as a result of the patient's postoperative treatment will

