Inclusion of 1-2 patients per week is expected corresponding to duration of inclusion of approximately 24 months. Inclusion: Planned to go on in the period from February 2015 to February 2017. Inclusion of patients will be stopped when the desired number of patients is achieved. The trial will be counted as concluded, when the last patient has registered with the primary endpoint.

Data analysis and reporting: from April to May 2017.

Ethical considerations:

Laparoscopic herniotomy is presently conducted at Gentofte Hospital with an intraabdominal pressure of 12 mmHg and sometimes with use of a small quantity of muscle relaxant for intubation.

It is not considered an inconvenience to use large doses of muscle relaxant, as the effect of this is fully reversed by sugammadex at the end of the anesthesia. Anesthesia and surgery will follow guidelines apart from the dosage of muscle relaxants.

We think that it is justifiable that information about the use of muscle relaxants/antidotes be stored in a sealed envelope in the patient record with respect to the blinding. There is an option to break the seal on the envelope in an emergency situation. Routinely unblinding of the included patients will be done after the operation. Sugammadex is considered active in the first 24 hours, but the intervention will be considered to be over.

The possible benefit in this trial is to investigate whether deep neuromuscular blockade gives better surgical space conditions at pneumoperitoneum 12mmHg in patients > 18 years old undergoing laparoscopic umbilical, -linea alba and incisional herniotomy.

Protocol
The hernia study
September 16. 2016

Informed consent will be obtained before the patients arrive to the operation ward. We thereby wish to avoid having the patient make a decision about participation in the trial, in the stressed environment an operation ward is often experienced as for a patient before an operation. The inclusion and exclusion criteria used will ensure that we only investigate patients who will be able to tolerate being treated according to the two strategies. Intervention with respect to possible complications from this, are not unchanged either.

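### The clause exempting typical anaesthetic events from registration has no attribution or seriousness condition, and conflicts with the protocol's AE definition and final safety list

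*Combined protocol and SAP*

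**What the plan says.** The section *Side effects/events that will not be registered* contains four exclusions.

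- A general one, introduced as holding in general: "side effects and events that are typically seen in connection with the normal course of anesthesia and operation will not be registered". The sentence goes on to mention reporting to the Danish Medicines Agency.
- A haemodynamic one: "In this protocol side effects/events (AE) will be defined in the form of expected changes in pulse and blood pressure", followed by a threshold under which values "that deviate less than +/- 30% of the starting level will thus be accepted and not registered".
- One for surgical causes: "Side effects/events that may be ascribed to the operation with certainty", with wound pain and wound infection as examples.
- One for postoperative treatment, again only where that cause is certain.

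Three other parts of the protocol bear on the same events. *Reporting Procedures for Exchange of Adverse Event Information*, item (i), defines an AE as "any untoward medical occurrence in a Study subject who is administered the Study Drug regardless of whether or not a causal relationship" exists. The paragraphs on local reporting and the final list, which follow the exclusions, say that all AR, AE, SAR, SAE and SUSAR are collected on one list for the ethics committee and the agency. They then say that this list holds the registered events. *Risks, side-effects and events* gives the expected side effects of sugammadex, among them "Anesthesia complication" in the 1-10% row, without defining the term.

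**The concern.** The general clause sorts events by how usual they are under anaesthesia, not by what may have caused them. Rocuronium and sugammadex are given as part of the anaesthetic, as is mivacurium when it is used, so a reaction to one of them can look like an ordinary anaesthetic event. An investigator who suspects such a reaction finds one section that calls it an AE and another that tells them not to register it.

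What is at stake is how complete the safety list is. The *Ethical considerations* section says "It is not considered an inconvenience to use large doses of muscle relaxant", on the ground that sugammadex reverses the effect. Readers of the trial will look to the safety list, among other data, to see whether that view held up. A list from which expected reactions to the study drugs may be missing supports it less well.

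**Working it through.** There is no design figure to reproduce, and no arithmetic applies. The check compares the conditions in each exclusion and then follows one event through the protocol.

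**Conditions in each exclusion**

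| Exclusion | What it tests | Attribution condition | Seriousness condition |
|---|---|---|---|
| Typical of anaesthesia and operation | How usual the event is | None | None |
| Pulse and blood pressure under 30% | Size of the deviation | None in the threshold; the sentence before it refers to the anaesthesia | None |
| Caused by the operation | Cause | Must be certain | None |
| Caused by postoperative treatment | Cause | Must be certain | None |

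The last two rows protect a suspected drug reaction: if the study drug might be the cause, another cause is not certain and the event is registered. The first two rows give no such protection. The reference to anaesthesia in the second row does not supply it, because the study drugs are given during the anaesthetic.

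**Following one event.** Take an expected, non-serious reaction that the investigator suspects is due to sugammadex, of a kind often seen under anaesthesia.

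1. Under item (i) of the Reporting Procedures it is an AE.
2. Under *Registration of adverse events*, all events are followed to a diagnosis or cause and entered on the CRF.
3. Under the general clause it is not registered. Steps 2 and 3 contradict each other.
4. Item (ii) of the Reporting Procedures covers SAEs, SUSARs and device matters, so it does not apply. Item H covers serious reactions and unexpected non-serious reactions, so it does not name this one. Item (iii) applies only if MSD chooses to define non-serious events of interest. Item (vi) could carry it as other relevant safety information, but to MSD and not to the final list.
5. The final list is to hold all AR and AE, yet contains registered events only. If step 3 is followed, the event is absent.

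A pulse or blood pressure change under the 30% limit that is suspected to be a drug effect takes the same path, because the limit looks only at the value.

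**What is not lost.** An SAE goes to MSD within two business days and to the sponsor/investigator at once. An unexpected non-serious reaction goes to MSD within 2 working days. What remains is mainly the expected, non-serious reaction that resembles routine anaesthesia.

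**The case against.** The strongest reply is that the clause is narrower than it looks. It is hedged as a general rule, and the text that follows spells out the anaesthetic part only as changes that "will be defined in the form of expected changes in pulse and blood pressure as a result of the anesthesia". On that reading only minor haemodynamic variation is left out. The sentence that seems to redefine AE stands under a heading about non-registered events, so it most naturally gives an example of them. The clause also mentions reporting to the agency, so it might be read as dealing with that alone. In addition, the protocol looks actively for events: observation in hospital, telephone calls on days one and seven, and case-file review.

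Much of this stands. The narrow reading is reasonable, and the definition sentence is probably awkward drafting, not a deliberate rival definition. But the narrow reading still leaves a drug-suspected change under 30% unregistered. The later exclusions in the same paragraph speak of not registering, so agency reporting is not the whole matter. The search for events finds them but does not say which are exempt once found.

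Three stronger readings are tempting, and the documents do not support them.

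- *Events are dropped whatever their cause.* The clause is silent on cause; it does not say that cause is irrelevant.
- *The listed "Anesthesia complication" is excluded.* The term is undefined, and a complication is arguably a departure from the normal course. It may be caught, but the documents do not show that it is. The other listed effects (taste disturbance, consciousness during anaesthesia, allergic reactions) are not clearly caught either.
- *The safety list is the only evidence on reversal.* Neuromuscular monitoring continues until TOF exceeds 0.90, stable over 2 minutes, and TOF values are recorded. Abdominal contractions and the need for additional blockade are recorded as well.

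**Conclusion.** The inconsistency is real and minor. As written, the general clause and the 30% rule let an expected, non-serious reaction to a study drug go unregistered, contrary to the protocol's own AE definition and to its promise of a complete final list. This rests on the assumption that some investigators would apply the clause as it reads, not in its narrower sense; the text permits both.

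No count of lost events can be derived. A reader might apply the 1-10% row to 34 patients and infer 34 × 0.01 = 0.34 to 34 × 0.10 = 3.4 missing events. That product counts expected occurrences of an undefined side effect, not unregistered ones. It also assumes that all 34 patients receive sugammadex, although the protocol gives placebo reversal when TOF is above 0.90.

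The primary outcome, the sample size and the comparison of treatments are unaffected.

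**What to change.** Make three changes to the section on events that will not be registered.

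1. Limit the general clause, and the pulse and blood pressure rule with it, to non-serious events that are not suspected to be related to rocuronium, sugammadex or mivacurium.
2. State that any side effect listed in *Risks, side-effects and events* is registered, even if it is also common under anaesthesia. That list covers sugammadex only, so for the other two drugs the suspicion condition in item 1 does the work.
3. Reword the pulse and blood pressure sentence as an example of events that are not registered, and keep item (i) of the Reporting Procedures as the single definition of an AE.

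The final list can then hold all AR and AE other than those exempted by a stated and narrow rule. The cost is two or three sentences and a few more CRF entries. Treatment, sample size and analysis do not change.
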